2.2 STUDY OBJECTIVES

What are the real-world treatment patterns, patients' characteristics, clinical outcomes, and healthcare resource utilisation associated with palbociclib treatment in the 2 years following initiation in United Kingdom patients with hormone receptor-positive, human epidermal growth factor 2-negative metastatic breast cancer treated as part of the IPP?

Primary objectives:

- *To describe patient demographic and clinical characteristics at initiation of palbociclib.*

Secondary objectives:

- *To describe treatment pattern (as per licence/IPP requirement); including the proportion of patients with dose modification and who switch treatment 1, 2 and 3 years after palbociclib initiation, and median time to dose modification and treatment discontinuation ('drug survival'). For patients who progress, to describe the 1st/2nd /3rd line of treatment after progression.*
- *To describe overall survival and progression-free survival, response (complete response [CR], partial response [PR]), stable disease. This includes estimating*

PFIZER CONFIDENTIAL

the proportion of patients achieving those endpoints at 1, 2 and 3 years following palbociclib initiation; median survival, time to response and duration of response. In patients who respond to treatment, to describe PR and CR using “swimmer plots”.

- *To describe the occurrence of neutropenia during the first-year post-initiation observation period.*
- *To describe the occurrence of gastro-intestinal toxicity, including diarrhoea, nausea and vomiting during the first-year post-initiation observation period.*
- *To describe progression of clinical indicators, including biochemical and radiological indicators at each time-point available during the first year following palbociclib treatment initiation (e.g., full blood counts, liver function tests, bone profile).*
- *To describe breast cancer related healthcare resource utilisation (hospital admissions, outpatient visits, calls to Cancer National Services and contacts with the Acute Oncology Service) during the first year following palbociclib initiation.*

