Secondary Objective 2: To describe overall survival and progression-free survival, response (CR, PR), stable disease. This includes estimating the proportion of patients achieving those endpoints at 1, 2 and 3 years following palbociclib initiation; median survival, time to response and duration of response. In patients who respond to treatment, to describe PR and CR using "swimmer plots".

- Proportion of patients at 2-years following initiation of palbociclib who:
 - Are free from disease progression.
 - Are alive
 - Achieved PR
 - Achieved CR
 - Had stable disease
- Median (95% confidence interval [CI]):
 - PFS

PFIZER CONFIDENTIAL

- OS
 - Time to achieving best overall response
- Length of follow-up
- Best response to palbociclib, overall and by de novo and relapse status
- Time to best response – by de novo and relapse status
- Time to first response – overall and by de novo and relapse status

Secondary Objective 3: To describe the occurrence of neutropenia during the first-year post-initiation observation period.

- In the 6 months post-palbociclib initiation, proportion of patients who experience,
 - Neutropenia (overall and by grade, recorded and inferred from ANC measurements).
 - Worst neutropenia experienced within 3 months of palbo initiation
 - Febrile Neutropenia.

[figure not shown]
Secondary Objective 4: To describe the occurrence of gastro-intestinal toxicity, including diarrhoea, nausea and vomiting during the first-year post-initiation observation period.

- For each cycle, proportion of patients who experience Gastro-intestinal toxicity, including:
 - Diarrhoea.
 - Severity
 - Nausea.
 - Severity
 - Vomiting.
 - Severity
- Proportion of patients experiencing an AE during follow-up

Secondary Objective 5: To describe progression of clinical indicators, including biochemical and radiological indicators at each time-point available during the first year following palbociclib treatment initiation.

- Summary measures of full blood counts in the first 6 months following initiation:
 - Haemoglobin.
 - White cell counts.
 - Absolute neutrophil counts.
 - Platelet counts.
- Summary measures of liver function tests in the first 6 months following initiation:
 - aspartate transaminase (also called aspartate aminotransferase).
 - alanine transaminase (also called alanine aminotransferase).
 - alkaline phosphatase.
 - Albumin
 - Bilirubin

PFIZER CONFIDENTIAL

[figure not shown]

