- Summary measures of bone profile in the first 6 months following initiation:
 - Calcium.
 - Phosphate.
- Summary measures of urea and electrolytes in the first 6 months following initiation:
 - Creatinine
 - Potassium
 - Sodium
 - Urea
- Summary measures of radiological indicators in the first 6 months following initiation including the proportion of patients with:
 - Stable disease.
 - Progressive disease.
 - CR or PR.

Secondary Objective 6: To describe BC-related healthcare resource utilisation during the first year following palbociclib initiation.

- Summary measures of hospital admissions for each line of therapy, including:
 - Proportion of patients with at least one inpatient admission recorded
 - Inpatient admissions per patient.
 - Elective or non-elective.
 - Reasons for admission (including day cases).
 - Length of stay per inpatient admission.
 - Proportion of patients with at least one outpatient visit recorded
 - Outpatient visits per patient.
 - Reason for outpatient visit
 - Type of HCP seen during outpatient visits
- Proportion of patients with at least one interaction with CNS
- Number of CNS interactions per patient
- Type of CNS interaction
- Reason for CNS interaction
- Proportion of patients with at least one interaction with AOS
- Number of AOS interactions per patient
- Type of AOS interaction
- Reason for AOS interaction

For the estimation of endpoints, *the following definitions will be implemented. PFS will be defined as the time from the date of palbociclib initiation to the date of first documented disease progression (as documented in the radiological assessment section of the eCRF) or death. OS will be defined as the time from the date of palbociclib initiation until death from any cause. Time to achieving best overall response will be defined in patients who respond to treatment as the time from the date of palbociclib initiation until*

PFIZER CONFIDENTIAL

achievement of the best overall response: CR, or PR if CR is not achieved during follow-up. Duration of response will be defined as the time from the date CR or PR was first documented (whichever is recorded first) to the date of first documented disease progression or death from any cause (whichever occurs first).

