Proposed: The proportion of patients developing neutropenia and febrile neutropenia in the first 6 months post-palbociclib initiation will be summarised as a binary variable (see section 8.1.3), while occurrences per patient will be summarised as a quantitative variable (see section 8.1.1). Analyses for occurrences of neutropenia will be analysed overall and sub-divided by grade. Incidences of neutropenia will be presented in two ways. Firstly, neutropenia in the 6 months post-palbociclib initiation will be presented. Absolute neutrophil count, recorded as part of full blood counts or as part of the neutropenia dataset collected, will be used to determine incidences of neutropenia according to the CTC version 2.0 criteria (http://www.eortc.be/services/doc/ctc/ctcv20_4-30-992.pdf]).

Only absolute neutrophil counts from the neutropenia dataset that are within 6 months of palbociclib initiation will be included. Secondly, incidences of neutropenia as recorded in the notes will be presented as a quantitative variable (see section 8.1.1). The time from palbociclib initiation to first incidence of neutropenia will be presented as a quantitative variable (see section 8.1.1) with the categories to be determined after visualisation of the data.

PFIZER CONFIDENTIAL

Actual: Neutropenia, overall and by grade, was presented from two different sources on the eCRF (as recorded in the notes and inferred from the ANC measurements recorded in the 6 months post-palbociclib initiation) as a categoric variable as per section 8.1.2.

Proportion of patients experiencing febrile neutropenia and the worst grade of neutropenia experienced within 3-months of palbociclib initiation were also presented as a categoric variable as per section 8.1.2.

8.2.5 Secondary Objective 4: To describe the occurrence of gastro-intestinal toxicity, including diarrhoea, nausea and vomiting during the first-year post-initiation observation period.

Proposed: The proportion of patients developing diarrhoea, nausea and vomiting in their first year will summarised as a categorical variable (see section 8.1.2), while occurrences per patient will be summarised as a quantitative variable (see section 8.1.1). All the above will be assessed at 1, 15 and 22 days into the treatment cycle, for each cycle, as well as after 1 year of follow-up post-initiation of palbociclib.

[figure not shown]

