	during follow-up in Full Analysis set			date of CR/PR to documented disease progression or death. 95% confidence intervals calculated for median.	otherwise exclude.
Proportion of patients experiencing neutropenia and febrile neutropenia for first year post-observation period	Full Analysis set	Secondary objective 3	Overall and by grade of neutropenia. Treatment Line	Summary statistics calculated (incl. Mean/Median/SD/IQR/Range) and frequency and percentages of proportions of patients with neutropenia and febrile neutropenia.	Excluded
Proportion and summary measures of patients experiencing gastro-intestinal toxicity during first year observation period	Full Analysis set	Secondary objective 4	Overall and Treatment Line	Summary statistics calculated (incl. Mean/Median/SD/IQR/Range) and frequency and percentages of proportions of patients with experiencing gastro-intestinal toxicity including diarrhoea, nausea, and vomiting.	Excluded
Summary measures of full blood counts in the first year of initiation	Full Analysis set	Secondary objective 5	Overall and Treatment Line	Summary statistics calculated (incl. Mean/Median/SD/IQR/Range) of haemoglobin, white cell counts, absolute neutrophil counts, and platelet counts. The mean, median, minimum, and maximum reading will be used where multiple tests are taken within the study period.	Excluded
Summary measures of liver function tests in the first year following initiation of palbociclib	Full Analysis set	Secondary objective 5	Overall and Treatment Line	Summary statistics calculated (incl. Mean/Median/SD/IQR/Range) aspartate transaminase, alanine transaminase and alkaline phosphatase. The mean, median, minimum, and maximum reading will be used where multiple tests are taken within the study period.	Excluded
Summary measures of bone profile in the first year of initiation	Full Analysis set	Secondary objective 5	Overall and Treatment Line	Summary statistics calculated (incl. Mean/Median/SD/IQR/Range) of calcium and phosphate. The mean, median, minimum, and maximum reading will be used where multiple tests are taken within the study period.	Excluded
Summary measures of radiological indicators in the first year of initiation	Full Analysis set	Secondary objective 5	Overall and Treatment Line	Frequency and percentages for proportions of patients with stable and progressive disease or CR or PR. Where there is more than one test, the first, most common and most favourable test results will be used.	Excluded

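### Neutropenia, laboratory and radiology summaries stop at 6 months in the SAP, while Objectives 3 and 5 and table 8.2.9 still promise the first year

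*SAP*

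**What the plan says.** The objectives are set over one year. SAP 2.2 gives Objective 3 as "To describe the occurrence of neutropenia during the first-year post-initiation observation period", and the section 6 heading for Objective 5 refers to "radiological indicators at each time-point available during the first year following palbociclib treatment initiation". Protocol section 8 and the endpoint table in protocol 9.3 use the same year. Table 8.2.9 repeats it for neutropenia ("Proportion of patients experiencing neutropenia and febrile neutropenia for first year post-observation period"), blood counts, liver function, bone profile and radiology.

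The endpoint list in SAP section 6, which the SAP says reflects what was actually analysed, uses six months. The neutropenia bullet opens "In the 6 months post-palbociclib initiation, proportion of patients who experience" and covers febrile neutropenia as well as "Neutropenia (overall and by grade, recorded and inferred from ANC measurements". Every laboratory panel has the same limit, and so does radiology: "Summary measures of radiological indicators in the first 6 months following initiation including the proportion of patients with".

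In 8.2.4, the Proposed paragraph says "Only absolute neutrophil counts from the neutropenia dataset that are within 6 months of palbociclib initiation will be included", and the Actual paragraph describes neutropenia "inferred from the ANC measurements recorded in the 6 months post-palbociclib initiation". In 8.2.6, the Actual paragraph limits the per-patient blood values to 6 months.

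**The concern.** A table produced under Objective 3 or 5 would carry a first-year objective while summarising six months. A reader of the report could take a 6-month proportion for a 12-month one. Months 7 to 12 of the laboratory, radiology and neutropenia experience would not appear in these tables at all. The SAP refers in general terms to decisions by the Chief Investigator and the sponsor, but gives no reason for this particular change.

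Some windows are also missing. The Actual paragraph of 8.2.4 states none for notes-recorded or febrile neutropenia, and the Actual paragraph of 8.2.6 states none for radiology. The analyst has to choose between section 6 (6 months) and the heading above the paragraph (first year).

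**Working it through.** The study is descriptive and has no sample-size or power figure to reproduce. The check is a comparison of the stated windows, followed by a count of what lies outside six months.

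**Windows side by side**

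| Item | Objective and heading | Table 8.2.9 | SAP section 6 | SAP 8.2.4 / 8.2.6 Actual |
|---|---|---|---|---|
| Neutropenia inferred from neutrophil counts | first year | first year | 6 months | 6 months |
| Neutropenia recorded in notes | first year | first year | 6 months | none stated |
| Febrile neutropenia | first year | first year | 6 months | none stated |
| Blood counts, liver function, bone profile | first year | first year | 6 months | 6 months |
| Radiology | first year | first year | 6 months | none stated |

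Section 8.2.4 Actual also reports worst grade within 3 months. Section 8.2.6 Proposed is mixed: it summarises blood results over 6 months, then adds an assessment after 1 year.

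**Size of the gap**

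Inputs: cycle length 28 days (protocol 9.3); blood counts on day 1 of each cycle, and on day 15 of cycles 1 and 2 (dataset tables in protocol Annex 3 and the SAP appendix). Assumption: uninterrupted cycles.

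- Six months: 365.25 / 2 = 182.6 days; 182.6 / 28 = 6.52, so 6 complete cycles.
- Twelve months: 365.25 / 28 = 13.04, so 13 complete cycles.
- Day-1 samples at days 0, 28, 56 and so on: 7 before day 182.6 and 14 before day 365.25 (13 if the day-364 sample is left out).
- Adding the two day-15 samples, both early: 7 + 2 = 9 of 14 + 2 = 16 fall inside six months. Sampling is therefore somewhat front-loaded, but 7 of 16 planned samples still fall outside.

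**Any-grade neutropenia**

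Protocol section 7 cites 80.6% from pooled trial data and places onset soon after the start of therapy. Assume, for illustration only, that 80.6% is the 12-month incidence.

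- Constant hazard: 1 − (1 − 0.806)^0.5 = 0.56 by 6 months.
- All first events early: 80.6% by 6 months.

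The loss from stopping at 6 months lies between about 25 percentage points and none. The protocol's description of early onset points to the small end.

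**Are later data planned?**

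Both dataset tables call for blood counts and liver enzymes on day 1 of each cycle, without a 6-month stop. They call for calcium and phosphate at each cycle through the first year. They do not list albumin, bilirubin, or the urea and electrolyte tests that section 6 adds, so for those the documents do not show what was to be collected beyond 6 months.

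**The case against.** The strongest reply is that the SAP discloses the shorter window. Section 6 labels each affected bullet 6 months. Section 8.2 says that proposed analyses which were not run are kept there as a record, and table 8.2.9 sits in that section with other outdated text. Protocol 9.7 lets the SAP change plans and requires an amendment only for major changes to primary endpoints. This stands in part: a reader might infer a procedural breach, and the documents do not support that. But the first-year wording is not confined to the table. It remains in SAP 2.2 and in the section 6 headings directly above the 6-month bullets. Nor does the table simply preserve the proposed plan, because the Proposed paragraph of 8.2.4 already uses 6 months.

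Four stronger readings are tempting and should not be drawn.

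- *The two neutropenia sources are not comparable.* Section 6 puts both under one 6-month bullet. Section 8.2.4 Actual is only silent on the notes-recorded window. That calls for clarification and does not show a mismatch.
- *The cited median progression-free survival shows how much progression is missed.* That calculation counts first progression or death. The Objective 5 radiology summary uses a first, modal or most favourable result per patient (8.2.6 and 8.2.9), so the calculation does not measure the effect on this table.
- *Progression and response are understated.* A proportion labelled 6 months is not an understated 12-month proportion. Objective 2 reports progression-free survival, best response and time to response beyond 6 months. The cover is only partial, because 8.2.3 Actual gives its proportions at 2 years only.
- *The later data are in hand.* Collection is planned, but from routine records and as clinically indicated, and the documents do not show that extraction went past 6 months.

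**Conclusion.** The contradiction is real. Objectives 3 and 5 keep a first-year window in the objectives, headings and table 8.2.9, while the endpoint list stops at 6 months for every item, as do 8.2.4 for count-based neutropenia and 8.2.6 for blood values. The objectives are answered for about half of the stated window: 6 of 13 complete cycles, assuming uninterrupted 28-day cycles. Months 7 to 12 are not summarised in these tables. For radiology the 6-month limit appears only in section 6, and for notes-recorded and febrile neutropenia 8.2.4 Actual gives no window, so these places need reconciling.

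The practical effect is moderate. Any-grade neutropenia probably changes little, given the early onset that the protocol describes. The laboratory and radiology summaries lose more of their stated period. The documents do not allow the change in those tables to be estimated.

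**What to change.** Set the window to 12 months from index in SAP sections 6, 8.2.4 and 8.2.6, stated explicitly for both neutropenia sources, febrile neutropenia, the laboratory panels and radiology. Use the day-1-of-each-cycle data that the dataset tables call for. Keep the 6-month results and the 3-month worst grade as additional rows.

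First confirm how far extraction went for each panel. Where data beyond 6 months were not extracted, relabel Objectives 3 and 5, the section headings and table 8.2.9 as 6 months for those items, state the reason, and report the deviation from the protocol.

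The cost is SAP wording, a re-run and slightly larger tables if the data are held. The relabelling route costs only text, but leaves months 7 to 12 undescribed.

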Secondary objective: To describe overall survival and progression-free survival, response (CR, PR), stable disease. This includes estimating the proportion of patients achieving those endpoints at 1, 2 and 3 years following palbociclib initiation; median survival, time to response and duration of response. In patients who respond to treatment, to describe PR and CR using "swimmer plots".

 Proportion of patients at 1, 2 and 3 years following initiation of palbociclib who: 
 Are free from disease progression. Are alive Achieved PR Achieved CR Had stable disease Median (95% confidence interval [CI]) : 
 PFS OS Time to achieving best overall response Summary measures of duration of response (Kaplan-Meier analysis). Representation of all radiological assessment of response (CR / PR / no response or stable disease / progressive disease) in patients responding to treatment (achieving CR or PR following initiation of palbociclib) using “swimmer plots”. 	
 Date ((DD/MM/YYYY) unless specified otherwise) of start and end of palbociclib. Date of data collection. Patient status at the end of data collection period (alive/dead): 
 Date of death / last clinic visit. If not known (i.e. lost to follow-up), date of last recorded hospital visit. Radiological assessments of response during the follow-up period: date of assessment and outcome (CR / PR / no response or stable disease / progressive disease), as documented by the local investigator.

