The following definitions will be implemented. PFS will be defined as the time from the date of palbociclib initiation to the date of first documented disease progression (i.e. mention of disease progression or mixed response in the medical records, e.g. due to evidence of a new site of disease, or increasing disease, after treatment initiation) or death. OS will be defined as the time from the date of palbociclib initiation until death from any cause. Time to achieving best overall response will be defined in patients who respond to treatment as the time from the date of palbociclib initiation until achievement of the best overall response: CR, or PR if CR is not achieved during follow-up. Duration of response will be defined as the time from the date CR or PR was first documented (whichever is recorded first) to the date of first documented disease progression or death from any cause (whichever occurs first).

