9.7. Data analysis

Detailed methodology for summary and statistical analyses of data collected in this study will be documented in a separate statistical analysis plan (SAP), which will be dated, filed and maintained by the sponsor. The SAP may modify the plans outlined in the protocol; any major modifications of primary endpoint definitions or their analyses would be reflected in a protocol amendment.

Analyses will be performed by pH Associates using Stata (StataCorp LLC) and R. Data from all participating centres will be pooled for analysis.

According to the objectives, descriptive statistics will be presented using data at 1 year (using retrospective data collected) or 2 and 3 years (using the prospective data as well as the retrospective data collected) following initiation of palbociclib. Clinical measurements will be presented at each time-point available, as described in section 7.3. The interim study report will only present results for objectives which are relevant to the 1-year follow-up period and the final report will present results for objectives which are relevant up to the 3-year follow-up period.

Descriptive statistics (numbers, percentages, means, standard deviations [SD], medians, quartiles, minimum, and maximum), as appropriate to the data collected, will be used to describe baseline demographic and clinical characteristics for the overall study. Treatment patterns and hospital admissions will also be reported using descriptive statistics. The frequency and proportion of patients experiencing a neutropenia, febrile neutropenia event;

and gastro-intestinal toxicity including diarrhea, nausea and vomiting, during follow-up, will be presented.

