2 INTRODUCTION

Note: in this document any text taken directly from the non-interventional (NI) study protocol is *italicised*.

Palbociclib was recommended for use with an aromatase inhibitor in patients with locally advanced and metastatic breast cancer (MBC) in the NHS in England by the National Institute for Health and Care Excellence (NICE) in November 2017 and by the Scottish Medicine Consortium (SMC) in December 2017^{1,2}. In order to provide access to palbociclib in the UK during the NICE/SMC appraisal period, the Ibrance® Patient Program (IPP) was run by Pfizer between April 2017 and November 2017 for England and Wales, and December 2017 for Scotland. The IPP provided free access to treatment to NHS patients with previously untreated (or >12 month since discontinuation of adjuvant or neoadjuvant treatment with a nonsteroidal aromatase inhibitor), Hormone Receptor Positive (HR+)/Human Epidermal Growth Factor 2 Negative (HER2-) MBC³.

Pfizer are interested in the opportunity to collect data from patients who received palbociclib as part of the IPP, to better understand effectiveness and safety of palbociclib when used in routine care in a UK context, with a focus on treatment persistence and dose management, patients' characteristics, clinical outcomes, and healthcare resource utilisation. This study will evaluate patients' clinical progression and experience of treatment with palbociclib in routine clinical practice in the UK. This study may be of benefit to the NHS and patients in supporting assessments of the benefit of palbociclib in routine care; and will also help contextualise evidence on safety of palbociclib previously generated from the real-world studies in US populations.

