6 ENDPOINTS AND COVARIATES

The following endpoints will be estimated for the final report. Additional endpoints evaluated as a result of decisions made by the CI and Pfizer have been italicized. This list is designed to reflect the analyses conducted.

Primary Objective: To describe patient demographic and clinical characteristics at initiation of palbociclib.

- Age at initiation of palbociclib.
- Distribution of treatment lines
- Time to letrozole – 1st line palbociclib group
- Sex (male/female)
- Ethnicity of patients initiated on palbociclib.
- Menopausal status at initiation of disease
- Menopausal status at recurrence of disease
- Menopausal status at diagnosis of metastatic disease
- Disease free interval
- Summary measures of MBC history, including:
 - Whether cancer is primary or recurrent diagnosis.
 - Site and grade of disease.
 - Lymph node involvement (including number of lymph nodes) at initial BC diagnosis and by de novo status
 - Oestrogen-receptor, progesterone-receptor and HER2 status at initiation of disease

PFIZER CONFIDENTIAL

- Oestrogen-receptor, progesterone-receptor and HER2 status in the metastatic setting
- Proportion of patients (non de-novo metastatic only) who had a rebiopsy
- Oestrogen-receptor, progesterone-receptor and HER2 status at recurrence of disease out of those patients who were rebiopsied.
- Tumour stage at initial disease diagnosis and by de novo status
- Nodal status at initial disease diagnosis and by de novo status
- Metastatic at initial disease diagnosis and by de novo status
- Tumour size at initiation of disease and by de novo status
- Tumour grade at initiation of disease and by de novo status
- Proportion of patients who had Ki67 measured
- Summary of Ki67 values out of those patients with Ki67 measured.
- ECOG performance score at initial disease diagnosis
- ECOG performance score at recurrent disease diagnosis
- ECOG score at metastatic diagnosis
- Type of recurrence
- Number of metastatic sites.
- Location of metastases
 - Non-visceral location of metastases
 - Metastatic sites with locoregional recurrence
- Duration of BC disease at initiation of palbociclib.
 - Defined as date of diagnosis to date of initiation of palbociclib.
- Treatment history of MBC
 - Proportion of patients treated with chemotherapy in the neoadjuvant or adjuvant setting
 - Chemotherapy name
 - Proportion of patients treated with chemotherapy in the advanced/disease modification/metastatic setting
 - Chemotherapy name

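### SAP section 6 reads PFS progression only from the radiological section of the eCRF, and does not record or explain this departure from the wider definition in protocol 9.3

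*SAP*

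**What the plan says.** Protocol 9.3 runs PFS from palbociclib initiation to first documented progression or death. It explains progression as "mention of disease progression or mixed response in the medical records, e.g. due to evidence of a new site of disease" or increasing disease. SAP section 6 keeps the sentence but replaces the explanation, so that PFS ends at the "date of first documented disease progression (as documented in the radiological assessment section of the eCRF) or death".

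Several other places bear on this:

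- **Authority to change.** Protocol 9.7 states that "The SAP may modify the plans outlined in the protocol". It ties a protocol amendment to major changes in primary endpoints, and PFS is secondary.
- **Variables for this objective.** Protocol 9.3 lists "Radiological assessments of response during the follow-up period: date of assessment and outcome" and no other source of progression.
- **A separate item.** The dataset tables in protocol Annex 3 and the SAP appendix each list progression sites and dates as an item of its own, apart from the response assessments.
- **Duration of response.** SAP section 6 runs it "to the date of first documented disease progression or death from any cause (whichever occurs first"), with no mention of the radiological section. The median PFS row in SAP 8.2.9 does not mention it either.
- **Where to find definitions.** SAP 8.2 sends the reader to section 8.1.3. That section describes frequency tables, Kaplan-Meier estimation and swimmer plots, and does not define progression.
- **Censoring.** Under SAP 8.2, patients alive without progression are censored at their last documented response assessment.

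**The concern.** The two definitions can give different event dates for the same patient. A progression noted in a clinic letter, or entered only in the progression item, is a PFS event under the protocol on the day it was recorded. Under SAP section 6 as written, one of three things happens to it. It is dated at a later radiological entry, it is counted only when the patient dies, or it is not counted and the patient is censored at the last response assessment.

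All three would generally push PFS upwards. The 2-year progression-free proportion moves the same way: each such patient alive at two years adds one to the numerator and leaves the denominator, patients known to be alive, unchanged.

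Nothing in the SAP tells a reader that the reported PFS differs from the protocol's. SAP section 1 speaks only in general terms of amendments to sections 6 and 8. SAP 8.2.3, which sets proposed against actual analyses for this objective, does not mention the change.

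**Working it through.** The plan states no figure for this point, so the check is mainly a comparison of text.

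**Step 1: what counts, and from where.**

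| Question | Protocol 9.3 | SAP section 6 |
|---|---|---|
| Source of progression | Medical records, any mention | Radiological assessment section of the eCRF |
| Mixed response | An event | Not mentioned |
| Separate progression item (Annex 3 / appendix) | Dates collected | Not used |
| Change recorded | n/a | No |

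The listed categories for a response assessment are "outcome (CR / PR / no response or stable disease / progressive disease"). Mixed response is not among them, and the SAP does not say how it is coded.

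**Step 2: illustration of size.** The share of events affected is not in the documents, so it is assumed. Inputs:

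- Median PFS of 24.8 months, from the phase III first-line trial quoted in protocol section 7.
- About 200 patients (SAP 2.1).
- Exponential PFS, which is an assumption.
- f, the share of all PFS events that are progressions recorded only outside the radiological section. Deaths without progression cannot be missed, so f is smaller than the corresponding share of progressions alone.

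Baseline: S(24) = exp(−ln 2 × 24/24.8) = 0.511. Without censoring, events by month 24 = 200 × (1 − 0.511), about 98.

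- *Lost:* treated as independent censoring, S(24) becomes 0.511^(1−f) and the median becomes 24.8/(1−f).
- *Delayed by d months:* S(24) becomes S(24) + f × [S(24−d) − S(24)], with S(21) = 0.556 and S(18) = 0.605.

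| f | Patients among 98 events | S(24), delayed 3 to 6 months: rise | S(24), lost | Median, lost |
|---|---|---|---|---|
| 0 | 0 | 0 | 51.1% | 24.8 |
| 5% | about 5 | 0.2 to 0.5 points | 52.9% | 26.1 |
| 10% | about 10 | 0.4 to 0.9 points | 54.7% | 27.6 |
| 20% | about 20 | 0.9 to 1.9 points | 58.5% | 31.0 |

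The route in which missed progressions are counted only at death falls between the two.

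For scale, ignoring censoring, the 95% CI half-width at 24 months is 1.96 × √(0.511 × 0.489/200) = 0.069, or about 7 points.

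**Step 3: the median on two-year data.** SAP 8.1 limits the analysis to two years of follow-up. Protocol section 7 also quotes a first-line median of 20.2 months. With f = 20% lost, this becomes 20.2/0.8 = 25.3 months, so a median reached within two years would no longer be reached. With f = 10% it is 20.2/0.9 = 22.4 months and is still reached.

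**The case against.** The strongest reply is that nothing has been narrowed. The protocol says what in the notes counts as progression, and the SAP says which eCRF section the date is read from. These could be one rule at two levels. The protocol's variable list supports this. So do the dataset tables, which describe an item with the same outcomes, also documented by the local investigator, but call it a clinical response assessment. That may be one item under two labels. This stands as a limit: the eCRF is not available, and the effect may be nil. It does not answer the lack of any statement in the SAP, or explain why a separate dated progression item is left unused.

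It is also fair that mixed response is mainly a gap in the protocol's own category list, that the assumed shares have no basis in the documents, and that this is a descriptive study with no hypothesis or decision rule.

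A reader might infer three stronger points. The documents do not support them.

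- **That the SAP presents the change as protocol wording.** SAP section 2 says that "any text taken directly from the non-interventional (NI) study protocol is *italicised", and in the extracted text the altered phrase is in italics. But the italics there are not a reliable guide. Verbatim protocol text in SAP 2.1, in section 7 and at the end of the same definitions paragraph is not italic. A site-selection criterion that differs from the protocol is. Section 6 also gives italics a second use: "Additional endpoints evaluated as a result of decisions made by the CI and Pfizer have been italicized".
- **That the change needed a protocol amendment.** Protocol 9.7 does not require one for a secondary endpoint.
- **That the SAP holds two rival definitions of PFS.** The summary table and duration of response are silent on the source. They can be read as shorthand for section 6.

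**Conclusion.** The point holds as one of disclosure and completeness. SAP section 6 uses a source of progression that is, as written, narrower than protocol 9.3. The choice is permitted and has some support in the protocol, but it is neither recorded nor explained. The separate progression item is not used, and section 8.2 points to a section without the definition.

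The direction is generally towards longer PFS. The size is unknown. It is nil if every progression is also entered in the radiological section, and small beside sampling error if missed progressions soon appear there. It becomes a material part of the CI half-width only if a sizeable share is lost. The percentages above rest on assumed shares, an exponential curve and medians from other trials, and say nothing about what happened in this cohort.

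Severity is minor to moderate, because the study is descriptive and PFS is a secondary endpoint.

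**What to change.** 1. In SAP section 6, state that PFS is radiology-based, that this departs from protocol 9.3, and why.
2. Report PFS under the protocol definition as a sensitivity analysis. The event is the earliest of radiological progression, a date in the progression item, mixed response where a date was recorded, or death. The SAP describes its actual analyses in the past tense, so label this analysis post hoc if they were already run. Give the number of patients whose event status or date differs between the two definitions. If that number is near zero, a footnote is enough.
3. Apply the same stated progression rule to the 2-year progression-free proportion and to duration of response, if it is reported. Correct the pointer in section 8.2 to section 6.

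The cost is a few lines of SAP text, one further Kaplan-Meier run and one count, from items the dataset already lists. Mixed response is not a listed field, so the protocol definition may be only partly recoverable. Chart-recorded progression is also less objective, and the PFS reported under it may be slightly less favourable.
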